### Specify Other Recruitment Method

Patients will be recruited (utilizing inclusion and exclusion criteria outlined above) through the Otolaryngology Faculty Practices and the Mount Sinai Data Warehouse list of COVID-19 positive patients diagnosed at Mount Sinai Hospital as well as the web based application *STOP COVID NYC* (IRB 20-03271).

### How Participants Will Be Identified

Participants who are > 18 years of age, have self-reported anosmia and a positive COVID-19 diagnosis will be identified through the Mount Sinai Otolaryngology Faculty Practices and through the web-based application *STOP COVID NYC* (IRB 20-03271).

### How Research Will Be Introduced to Participants

Once participants are identified, the attending physician or another member of the research team will reach out to the patient to discuss the study and obtain informed consent.

### How Participants Will Be Screened

Subjects will be recruited via the Otolaryngology Faculty Practices or the web-based application *STOP COVID NYC* (IRB 20-03271) who have consented to be contacted for future studies.

Participants will be screened for inclusion and exclusion criteria by the attending physician or another member of the research team during the same session that the research is being explained to the participant.

## **Risk and Benefits**

## Risks to Subjects

Patients will be randomized into treatment and control groups. The treatment group will receive omega-3-fatty acid supplementation (1000 mg of omega-3 fatty acid blend including 683 mg Eicosapentaenoic Acid and 252 mg Docosahexaenoic Acid) to be taken daily for 6 weeks. The control arm will receive a placebo pill to be taken twice daily.

The main risks to subjects that choose to participate are as following:

-BSIT: This 12-item version of the Smell Identification Test™ is useful for quantifying smell loss in situations where less than five minutes of time are available. The odors are well known in most cultures. There are no side effects known to occur from this test. Patients could theoretically experience some nausea, vomiting, or headache from the different smells.

-Omega-3 fish oil has been deemed "generally regarded as safe" by the Federal Drug Administration and is considered to be very rarely associated with significant adverse side effects. Side effects of omega-3 fatty acid supplementation are typically mild and include gastrointestinal discomfort, heartburn, headache, and unpleasant taste. Patients also sometimes note a fishy odor or taste in their mouth that they find unpleasant. Taking high doses of fish oil supplements can potentially increase the risk of bleeding. However this is associated with much higher dosing and duration than what will be utilized during this study. A 2018 Chang et al. meta-analysis of 21 randomized clinical trials involving a total of 12,750 patients receiving omega-3 fatty acid supplementation found no serious adverse events, concluding that they are generally safe and well-tolerated but are associated with these mild side effects. No patient-reported adverse events were reported in the 2020 Yan et al. randomized control study on omega-3 fatty acid supplementation after skull base surgery.

2 Chang, C. H. et al. Safety and tolerability of prescription omega-3 fatty acids: A systematic review and meta-analysis of randomized controlled trials. *Prostaglandins Leukot Essent Fatty Acids* 129, 1-12, doi:10.1016/j.plefa.2018.01.001 (2018).

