### Primary and Secondary Study Endpoints:

The primary endpoint of this study is a Brief Smell Identification Test, a standardized and validated objective measure of olfactory function, administered 6 weeks from symptom onset.

The secondary endpoints of this study include patient-reported outcome measure surveys, a modified Brief Questionnaire of Olfactory Dysfunction - Negative Statements (QOD-NS) survey and Sino-Nasal Outcome Test (SNOT-22), administered at time points of 1, 2, 4, and 6 weeks after symptom onset.

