## **Procedures**

### Description of the Study Design

This is a prospective, double-blind, randomized controlled trial.

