### Description of Procedures Being Performed

Patients will be recruited (utilizing inclusion and exclusion criteria outlined above) through the Otolaryngology Faculty Practices as well as the web based application STOP COVID NYC. Current recruitment goals are one hundred seventy six patients, with eighty eight patients in each group. After recruitment the patients will be block-randomized by a computer-generated sequence in a 1:1 allocation to treatment or control arms. Patients randomized to the treatment group will be allocated a supply of 1000 mg capsules of omega-3 fatty acid blend including 683 mg Eicosapentaenoic Acid and 252 mg Docosahexaenoic Acid) to be taken daily for 6 weeks. Patients randomized to the control group will receive a placebo and will follow the same regimen as the treatment group. Collection of data (described below) will occur through the use of the EPIC electronic medical record system, through phone conversations between investigators and subjects, and through information collected during office visits. The primary outcome studied will be the Brief Smell Identification Test (BSIT) which will be administered 6 weeks after symptom onset. The secondary outcomes include patient-reported outcome measure surveys, a modified Brief Questionnaire of Olfactory Dysfunction - Negative Statements (QOD-NS) survey and Sino-Nasal Outcome Test (SNOT-22), administered at time points of 1, 2, 4, and 6 weeks after symptom onset. After the conclusion of data collection a statistical analysis will be conducted to compare outcomes in the treatment and placebo arms.

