### **Safety Monitoring:**

Patients will be asked to report adverse effects related to omega-3 use. Minor side effects are not uncommon, and typically include gastrointestinal distress or fishy test. Serious adverse events are exceedingly rare. Patients will be instructed to report any potential adverse events to the PI which will be recorded. Patients will be screened for adverse events at each of the data collection check-points (1 week, 2 weeks, 4 weeks, and 6 weeks).

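### The active product has a recognisable fishy odour or taste, but the protocol states no sensory match for the placebo, so the self-reported secondary endpoints may be biased by patients recognising their arm.

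*Protocol*

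**What the plan says.** Under Description of the Study Design the protocol states: "This is a prospective, double-blind, randomized controlled trial".

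Risks to Subjects describes what the active product can feel like. It lists "gastrointestinal discomfort, heartburn, headache, and unpleasant taste" among the typical mild effects and adds: "Patients also sometimes note a fishy odor or taste in their mouth that they find unpleasant". Safety Monitoring goes further: "Minor side effects are not uncommon, and typically include gastrointestinal distress or fishy test". The last word is evidently meant to be taste.

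The two products are described differently. Under Description of Procedures Being Performed, patients in the active arm "will be allocated a supply of 1000 mg capsules of omega-3 fatty acid blend". In Risks to Subjects the comparator is described only by "The control arm will receive a placebo pill to be taken twice daily". The procedures section calls it simply a placebo on the same regimen as the treatment group. Neither section gives its content or says that it matches the capsule in form, appearance, odour or flavour.

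The secondary endpoints are "patient-reported outcome measure surveys, a modified Brief Questionnaire of Olfactory Dysfunction - Negative Statements (QOD-NS) survey and Sino-Nasal Outcome Test (SNOT-22"), collected at 1, 2, 4 and 6 weeks after symptom onset. The primary endpoint is the BSIT at 6 weeks from symptom onset, described as a validated objective measure.

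**The concern.** A double-blind comparison of self-reported scores is only as good as the patient's inability to tell the products apart. Here the protocol itself names a sensory cue specific to the active product and says nothing about how the control would reproduce or hide it.

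The setting makes this more than a routine blinding remark. Noticing a fishy odour or flavour needs some smell function. A patient on active treatment whose smell returns is better placed to recognise the product than one whose smell does not, so recognition can be tied to the outcome. Patients take the product at home (the Data section provides for mailing it), where they can inspect and smell it.

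QOD-NS and SNOT-22 are what the patient says about the symptoms. Someone who believes they are on the active product may score them more favourably with no true effect. A difference on these surveys could then not be separated cleanly from expectation.

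**Working it through.** **Step 1: the texts side by side.**

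| Feature | Active | Control |
|---|---|---|
| Form | capsules (procedures) | pill (Risks to Subjects); form not given (procedures) |
| Odour or taste | fishy odour or taste named as a side effect | not described |
| Masking of the cue | none described | none described |
| Frequency of intake | daily (both sections) | twice daily (Risks to Subjects); same regimen as active (procedures) |

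The last row is a contradiction within the protocol. It also bears on blinding, because two products taken at different frequencies are not indistinguishable.

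**Step 2: inputs for the size of a possible bias.**
- From the protocol: 88 per arm (2 × 88 = 176, the stated recruitment goal).
- Assumed, because the protocol gives no figure: two-sided 5% level, no dropout, survey score with SD 1 in each arm, no true effect. A share *f* of active patients recognise the product, and each of them shifts the reported score by *b* SD. Control patients do not shift.

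The protocol gives no power calculation behind 176, so there is no planned effect size to reproduce. For scale, the difference detectable with 80% power is (1.960 + 0.842) × √(2/88) = 0.42 SD.

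**Step 3: formulas.**
- False difference: Δ = f × b.
- Standard error, allowing for the extra spread in a part-shifted active arm: SE = √{[2 + f(1 − f)b²]/88}. Without the extra spread it is √(2/88) = 0.151.
- Probability of a significant result: 1 − Φ(1.96 − Δ/SE) + Φ(−1.96 − Δ/SE).

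**Step 4: results.**

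| f | b (SD) | Δ (SD) | Two-sided error |
|---|---|---|---|
| 10% | 0.25 | 0.025 | 5.3% |
| 20% | 0.3 | 0.06 | 6.8% |
| 40% | 0.3 | 0.12 | 12.4% |
| 20% | 0.5 | 0.10 | 10.1% |
| 30% | 0.5 | 0.15 | 16.6% |
| 50% | 0.5 | 0.25 | 37.2% |

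Worked example, second row: 0.20 × 0.3 = 0.06; 0.06/0.151 = 0.40; 1 − Φ(1.56) + Φ(−2.36) = 0.068. Ignoring the extra spread moves the third row to 12.5%.

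Relative to 0.42 SD, the false difference is 0.06/0.42 = 14% in the second row and 0.12/0.42 = 29% in the third. The answer depends almost wholly on *f* and *b*, and the documents supply neither.

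**The case against.** The strongest reply is that the protocol is silent on matching; it does not say the placebo is unmatched. It commits to double-blinding, calls the product a blinded intervention in its withdrawal rules, and puts the control group on the same regimen in the procedures section. Pill against capsules may be loose wording, and a product description may exist elsewhere, since the Drugs/Biologics heading has no text under it here. This stands. A reader might infer that the placebo is known to be generic and distinguishable, and the text does not support that. What remains is that the protocol names the cue and specifies nothing against it. That specification belongs in the protocol rather than in an analysis plan.

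The cue may also be rare or weak. Risks to Subjects cites an earlier randomised omega-3 trial after skull base surgery with no patient-reported adverse events, and patients with smell loss are less able than others to notice an odour at entry. Both points stand, and they are why the range must include a negligible bias. Safety Monitoring points the other way by calling minor effects not uncommon.

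Three further inferences are tempting and go too far:
- *Only recovered active patients can be unblinded.* Unpleasant taste, heartburn and gastrointestinal discomfort need not depend on smell, and the inclusion criterion is olfactory dysfunction, so some smell may remain at entry. A recovered control patient who notices no fishy taste may also guess the arm.
- *Nothing planned could reveal it.* Adverse events are screened at weeks 1, 2, 4 and 6, together with the surveys, so fishy-taste reports would be on record. They are a partial proxy, not a treatment guess.
- *The primary result is compromised.* The BSIT is an odour identification test and less exposed. The documents give no basis for quantifying an effect of expectation on it.

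**Conclusion.** The point holds as a gap in the blinding specification that affects the secondary, self-reported endpoints. The protocol claims double-blinding, names a sensory cue of the active product, and states neither a matching placebo nor any masking. Because noticing the cue depends partly on smell, recognition can be associated with recovery.

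The size cannot be fixed from the documents. On the assumptions above it runs from negligible (5.3% error) through moderate (about 7% to 12%) to serious (about 37%). No single value in that range should be read as an estimate. The calculation also uses one flat shift for everyone who recognises the product. Recovered patients may have less room to improve on smell-related items, which would reduce it; control patients inferring placebo and scoring worse would increase it.

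The change is worth making because it is cheap and protects the survey comparisons whichever end of the range is true.

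**What to change.** 1. In Risks to Subjects and in Description of Procedures Being Performed, specify a placebo capsule matched to the active capsule in appearance and in odour or flavour, with the same masking flavour in both products. If the product in use already meets this, a sentence saying so is enough.
2. Reconcile the regimens in Risks to Subjects (active daily, placebo twice daily) with the same regimen stated in the procedures section. The sponsor must settle which is meant; for blinding, what matters is that the sections agree and the arms cannot be told apart by how the product is taken.
3. Report fishy-taste adverse events by arm, from the screening already planned at weeks 1, 2, 4 and 6, beside the QOD-NS and SNOT-22 results.
4. Optionally, add one treatment-guess question with its reason (taste or smell, or feeling better). Ask it only after exposure has begun: the weeks are counted from symptom onset and the product is mailed, so a week-1 contact may come before any intake. An early guess misses later recoverers, and a late one is mixed up with benefit, so it supplements the matched placebo and does not replace it.

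The cost is a procurement specification, possibly a slightly dearer placebo, and one table by arm from data already collected.

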### Description of Procedures Taken to Lessen the Probability or Magnitude of Risks

Patients randomized to the treatment arm will be administered omega-3-fatty acid supplementation daily, as described previously. Patients will be provided a contact number to the research team to report any adverse effects and be directed to appropriate medical care. Patients may drop out of the study for any reason at any time.

### Provisions for Research Related Harm/Injury

Significant adverse reactions to treatment will lead to immediate termination of treatment. Medical care will be provided by a Mount Sinai physician or a physician of the participant's choosing. Participant insurance will be charged for medical care related to treatment.

### Expanded Direct Benefit to Subjects

Participants may not receive any benefit from participation in the study. There is a possibility that participants in the treatment arm regain a greater degree of olfactory function or experience recovery at a faster rate as the result of the intervention.

### Benefit to Society

Given the extent of the current COVID-19 outbreak and the high prevalence of anosmia in patients, it is important to gain an understanding of this symptomatology. As outlined in the background, olfactory dysfunction has been linked to impaired quality of life, higher rates of depression, and increased morbidity and mortality. The proposed study aims to elucidate the natural history of COVID-19 associated olfactory dysfunction and investigate omega-3-fatty acid supplementation as a potential therapeutic intervention. Such information will help guide future research and treatment of COVID-19 associated olfactory dysfunction.

### Provisions to Protect the Privacy Interests of Subjects

Data will be saved on a master list of subjects kept on a secure department-owned computer. Subjects will be deidentified and assigned a code, with which all other communication and data will be saved. Subjects will be able to decide whether or not to discuss their participation in the study with individuals outside of the research study. The patient will be able to decide what private information to disclose to research personnel provided the information is not necessary for the study. Additionally, subjects will be able to decide which research personnel they would like to communicate with. Study personnel will respect subjects' decisions. All saved data will be permanently destroyed at the end of this study.

### Economic Impact on Subjects

There is no anticipated cost to research subjects. The cost of omega-3-fatty acid treatment and the placebo control will be covered by the Division of Rhinology and Sinus Surgery within the Department of Otolaryngology - Head and Neck Surgery. All additional procedures and office visits are standard of care and do not incur any additional cost to the patient. Patients are

encouraged to call the Mount Sinai Otolaryngology FPA service phone system in case they experience any side effects.

## **Procedures**

### Description of the Study Design

This is a prospective, double-blind, randomized controlled trial.

### Description of Procedures Being Performed

Patients will be recruited (utilizing inclusion and exclusion criteria outlined above) through the Otolaryngology Faculty Practices as well as the web based application STOP COVID NYC. Current recruitment goals are one hundred seventy six patients, with eighty eight patients in each group. After recruitment the patients will be block-randomized by a computer-generated sequence in a 1:1 allocation to treatment or control arms. Patients randomized to the treatment group will be allocated a supply of 1000 mg capsules of omega-3 fatty acid blend including 683 mg Eicosapentaenoic Acid and 252 mg Docosahexaenoic Acid) to be taken daily for 6 weeks. Patients randomized to the control group will receive a placebo and will follow the same regimen as the treatment group. Collection of data (described below) will occur through the use of the EPIC electronic medical record system, through phone conversations between investigators and subjects, and through information collected during office visits. The primary outcome studied will be the Brief Smell Identification Test (BSIT) which will be administered 6 weeks after symptom onset. The secondary outcomes include patient-reported outcome measure surveys, a modified Brief Questionnaire of Olfactory Dysfunction - Negative Statements (QOD-NS) survey and Sino-Nasal Outcome Test (SNOT-22), administered at time points of 1, 2, 4, and 6 weeks after symptom onset. After the conclusion of data collection a statistical analysis will be conducted to compare outcomes in the treatment and placebo arms.

### Description of the Source Records that Will Be Used to Collect Data About Subjects

The EPIC electronic medical record used at the Mount Sinai Hospital and FPA will be used to collect subject data.

### Description of Data that Will Be Collected Included Long-term Follow-Up

Patient identifying information (which will be then de-identified and exchanged with a Subject ID), demographics, history of present illness, past medical history, past surgical history, medication list, medication allergies, Brief Smell Identification Test (BSIT) score, modified Brief Questionnaire of Olfactory Dysfunction - Negative Statements (QOD-NS) Score, and Sino-Nasal Outcome Test (SNOT-22) score. Patients will be followed for a period of six (6) weeks with repeat collections of interval patient history as well as QOD-NS and SNOT-22 survey scores at the one, two, four, and six week follow-up periods.

## **Consent**

### Where and When Consent Will Be Obtained

Patients who have been identified for the study and meet inclusion criteria and do not meet exclusion criteria will be contacted to discuss the research study by the attending physician or another member of the research team. They will be sent a copy of the consent form to read over. Due to the current pandemic and inability for individuals to attend the office in-person to sign the consent form, participants will have the opportunity to sign the consent form virtually.

### Waiting Period for Obtaining Consent

The participant will have the opportunity to spend time reading the consent form to learn more about the study. If the participant decides to enroll in the study, they may do so by calling the PI to schedule a time to sign the consent.

## **Data**

### Description of Health Information that Will Be Viewed, Recorded, Or Generated

1. Data at the initial visit will include:
2. Documentation that patient meets all inclusion criteria and no exclusion criteria
3. Patient Identifying information (DOB, Name, MRN) and a Subject ID will be assigned
4. Patient's home address will be obtained in order to send BSIT kit and placebo or supplement.
5. Demographic information including age, gender, race and ethnicity
6. Patient history - history of present illness (including presence of symptoms, onset and duration of symptoms, associated symptoms, past medical history, past surgical history)
7. Past medical history
8. Past surgical history
9. List of medications and medication allergies
10. Brief Questionnaire of Olfactory Dysfunction - Negative Statements (QOD-NS) Score
11. Sino-Nasal Outcome Test (SNOT-22) Score
12. Follow-up visits at 1 week, 2 weeks and 4 weeks:
13. Patient interval history
14. Brief Questionnaire of Olfactory Dysfunction - Negative Statements (QOD-NS) Score
15. Sino-Nasal Outcome Test (SNOT-22) Score
16. Follow-up visit at 6 weeks:
17. Patient interval history
18. Brief Smell Identification Test (BSIT) Score
19. Brief Questionnaire of Olfactory Dysfunction - Negative Statements (QOD-NS) Score

## 20. Sino-Nasal Outcome Test (SNOT-22) Score

Follow-up visits at 1 week, 2 weeks and 4 weeks:

1. Patient interval history
2. Brief Questionnaire of Olfactory Dysfunction - Negative Statements (QOD-NS) Score
3. Sino-Nasal Outcome Test (SNOT-22) Score

Follow-up visit at 6 weeks:

1. Patient interval history
2. Brief Smell Identification Test (BSIT) Score
3. Brief Questionnaire of Olfactory Dysfunction - Negative Statements (QOD-NS) Score
4. Sino-Nasal Outcome Test (SNOT-22) Score

### Description of Non-Health Information that Will Be Viewed, Recorded, Or Generated

Contact information including telephone number and email address.

### **Safety Monitoring:**

Patients will be asked to report adverse effects related to omega-3 use. Minor side effects are not uncommon, and typically include gastrointestinal distress or fishy test. Serious adverse events are exceedingly rare. Patients will be instructed to report any potential adverse events to the PI which will be recorded. Patients will be screened for adverse events at each of the data collection check-points (1 week, 2 weeks, 4 weeks, and 6 weeks).

